MCH nurses or other clinic staff will introduce the study and refer interested women to the study clinic after the ANC visit. (please see attached recruitment scripts) Study nurses will inform women about the study, answer any questions they have and invite women to participate in eligibility screening for the RCT. It will be emphasized that their participation would be completely voluntary and would not in any way affect their access to ANC, HIV, postnatal, or infant care services. In order to capture the proportion of women referred who meet our eligibility criteria and are interested in participating, a screening questionnaire will be used to collect data on eligibility. The screening questionnaire (attached) records no personally identifiable information. Oral consent will be obtained for participation of interested women in the screening phase. Eligible women will be invited to participate in the RCT. Those eligible women who decide not to participate will be asked for their reasons for non-participation, and these will be recorded in the screening questionnaire.

Eligibility: HIV- infected pregnant women will be recruited for the study. Women will be eligible if they are ARV naive, previously received ART or are currently on ART, have access to cell phone, ≥ 14 years and < 36 week gestation (Table 7).

To enhance generalizability, literacy will not be required if women have access to a partner or family member whom she would be comfortable to have read her the messages. This approach was developed in consultation with mothers in Kenya, who felt that involving their partner was acceptable and may engage more support. Eligible women will undergo screening, the informed consent process, and be randomized. Participants will be asked their preferences for message delivery including language, days of the week and time of the day.

Table 7: Layout of Phase 2 (RCT) procedures, study populations, and eligibility

RCT PHASE	
	Females
Population & maximum sample size	Women N=825
Study procedures	3-arm RCT
Topic	Compare unidirectional, bidirectional and no SMS
Recruitment	ANC

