Eligibility	
 • HIV-infected women \geq 14 years • Daily access to mobile phone and willing to receive SMS • Literacy not required if women have access to a partner/family member whom she would be comfortable to have read her the messages. • Expected continued residence in study area for the study duration • Willing to provide informed consent • Not enrolled in other studies

e) RANDOMIZATION PROCEDURES

Participants will be randomized to: 1) Simple unidirectional SMS messaging, 2) Interactive bidirectional SMS dialogue, and 3) Control, using 1:1:1 allocation. A computer-generated randomization list will be generated using random block sizes in STATA. The allocation codes will then be put in sequentially numbered sealed envelopes. Participants and study will be un-blinded to randomization arms.

f) DATA COLLECTION PROCEDURES

Women will be followed during pregnancy and for two years postpartum; all clinical care will be managed through the existing MCH and CCC infrastructure. Because the study aims to determine mHealth benefits in a routine clinic setting, specific ANC/PMTCT/HIV services will be delivered by the MOH programs with minimal clinic interactions with study personnel. The study team will abstract data regarding clinic attendance, pill refills, infant health and infant HIV status from the PMTCT program registry, labor and delivery ward, pharmacy and peer counselors registers. Viral load and infant HIV testing results will be abstracted from the national electronic viral load dashboard. We will make check-in calls to all participants regardless of study arm at 1 month and 1 year post-EDD. This will be done to ascertain mother's delivery status, infant status, and that phone number is up to date. Check-in calls will be done by data management teams and will call the participants contacts if they fail to reach study participant.

The study visit schedule will be: enrollment (any time in pregnancy), 6 weeks postpartum, then every 6 months up to 24 months. At each visit a standardized questionnaire will be administered using a tablet-based system (Open Data Kit, ODK) developed by the UW Department of

[figure not shown]

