While retention procedures will be minimized in order to avoid contamination of the intervention on retention outcomes, we will obtain phone numbers of contacts and conduct home visits after enrollment to ascertain locator information. This information will be used at the end of the RCT to conduct home visits to re-establish contact for participants who failed to return for appointments and are lost to follow up in order to ascertain 24-month postpartum outcomes. Participants who are not able to attend the 24-month visit at the clinic will have their 24-month visit procedures conducted at the home visit. Figure 6 illustrates study flow from enrollment to follow up.

In addition to collecting data from study participants during the trial, a facility survey will be conducted with a facility manager at each study site to collect information regarding facility characteristics, Option B+ implementation, human resources, service disruption and service management. The purpose is to identify whether facility-level factors associated with participant clinical outcomes. No human-subject data will be collected.

Figure 6: Consolidated Standards of Reporting Trials-CONSORT diagram of RCT design

We will collect patient information at baseline and follow-up visits using:

- Participant surveys: demographics, clinical and sexual history, family planning, disclosure, medication adherence, experience with SMS and technology, intimate partner violence, and depression
- Medical and pharmacy record extraction forms will be completed by data teams: delivery information, infant immunizations, maternal health, infant health, medication adherence, lab forms, pharmacy data, maternal mortality, and infant mortality.

- Viral load and infant HIV test results will be abstracted from the national electronic VL dashboard.

g) VARIABLES: Outcomes, indicators, and source documents

Table 8: RCT Outcomes

Primary Outcomes	Indicator	Source
Retention	Seen at scheduled visits	PMTCT register for scheduled visits
Drug Adherence	Number/ expected	Self-report, pharmacy 6 wk, 6, 12, 18, 24 mos
Maternal viral suppression	HIV RNA	Maternal blood at 6 wk, 6, 12, 18, 24 mos
Maternal drug resistance	OLA	Resistance assay in mothers with viral failure
Infant HIV	HIV testing: DNA on DBS and antibody	HEI register week 6, infant specimens
Infant HIV-free survival	HIV DNA, antibody and mortality	HEI register week 6, Infant specimens 6, 12, 18, 24 mos; verbal autopsy

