## 5.6 SAFETY MONITORING

Adverse and severe adverse events, including social harms such as violence or breach of confidentiality, will be monitored, and unblinded results will be reviewed by the DSMB. The DSMB will make recommendations regarding any imbalances in safety outcomes.

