**Table 5.3 Adverse and severe adverse events: shell table**

SAE #	PTIDNO	SAE description	Severity (Grade)	Onset date	Duration (days / unresolved)	Onset since randomization (days)	Relatedness to study

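### Intimate partner violence is surveyed and violence is named as a harm, but the SAP plans no by-arm report of it

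*Protocol*

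**What the plan says.** **Collection.** Protocol Phase 2, section f (Data collection procedures), introduces the survey list with "We will collect patient information at baseline and follow-up visits using", and the participant surveys include "experience with SMS and technology, intimate partner violence, and depression". Section i (Data collection instruments) repeats the topic. Section f also says "At each visit a standardized questionnaire will be administered using a tablet-based system". Visits are at enrolment, 6 weeks postpartum, then six-monthly to 24 months. No restriction by arm is stated.

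**Harm.** SAP section 5.6 says "Adverse and severe adverse events, including social harms such as violence or breach of confidentiality, will be monitored" and that "unblinded results will be reviewed by the DSMB". The DSMB is to make recommendations on imbalances in safety outcomes. No statistic, denominator or method is given.

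**Output.** SAP Table 5.3 is the only safety shell. Its columns are an event number, participant ID, "SAE description", grade, onset date, duration, days since randomisation and relatedness.

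**Exposure.** Protocol Phase 2, section d (Recruitment procedures), says "literacy will not be required if women have access to a partner or family member whom she would be comfortable to have read her the" SMS texts. SAP Table 5.1 has baseline rows for sharing a phone, reading SMS unassisted and disclosure of HIV status to the partner.

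**The concern.** The plan identifies a harm, and the Protocol collects a structured measure close to it in a randomised comparison, but the SAP does not connect the two. An imbalance is a difference between arms in a rate. An event listing with neither arm nor denominator cannot display one.

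At stake is what the trial report can say about safety. The intervention reaches women through phones that some of them share, and some messages may be read out by a partner. The Protocol presents it as a strategy that could be scaled up. A by-arm IPV estimate produced only after the data are seen, in an unblinded trial, would carry less weight than one laid down in advance. If none is produced, readers get no estimate of the effect on violence.

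**Working it through.** **1. Trace IPV through the documents.**

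| Place | Is IPV or violence there? |
|---|---|
| Protocol Phase 2, sections f and i, survey topics | Yes |
| Protocol Table 8, RCT outcomes | No (its secondary outcomes are headed as selected) |
| SAP section 2 and Table 2.1, endpoints | No |
| SAP Table 5.1, baseline shell | No |
| SAP section 5.3, analyses | No |
| SAP Table 5.2, endpoint shell | No |
| SAP section 5.4, interim analysis | No (virologic outcomes and infant HIV-free survival only) |
| SAP section 5.6, safety monitoring | Violence named; no method |
| SAP Table 5.3, safety shell | Event listing; no arm, count, denominator or rate |

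The measure is collected and the harm is named, but no planned output joins them.

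**2. Reproduce the plan's own sample size.** This fixes the number of women available. Inputs from SAP section 3a: 75% v 85%, two-sided alpha 5%, power 80%.

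n = [1.96 × √(2 × 0.80 × 0.20) + 0.8416 × √(0.75 × 0.25 + 0.85 × 0.15)]² / 0.10²
= (1.1087 + 0.4724)² / 0.01 = 250 per arm.

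This matches the SAP table, and 250 × 1.10 = 275 is the planned size. Allowing for the plan's 10% attrition, 275 × 0.90 = 247.5, or about 248 women per arm.

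**3. Precision of a by-arm IPV comparison.** The documents give no IPV rate, so a control proportion p of 5% to 20% is assumed. Take one yes/no answer per woman and the same p in both arms:

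half-width = 1.96 × √[p(1 − p)(1/n₁ + 1/n₂)]

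| Control IPV (assumed) | One SMS arm v control (248 v 248) | Either SMS arm v control (496 v 248) |
|---|---|---|
| 5% | 3.8 points | 3.3 points |
| 10% | 5.3 points | 4.6 points |
| 20% | 7.0 points | 6.1 points |

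For example, at 10%: 1.96 × √(2 × 0.09 / 248) = 0.053.

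**4. What could be detected.** With 248 per arm, two-sided 5% and 80% power, the smallest detectable rise in one SMS arm is from 5% to 12.0%, 10% to 18.9%, or 20% to 31.0%. For either SMS arm v control it is 5% to 11.1%, 10% to 17.7%, or 20% to 29.5%. Power for a doubling in one SMS arm is 56% from 5%, 88% from 10%, and above 99% from 20%.

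**5. Sensitivity to survey completion.** SAP Table 6.1 reports more than 40% missing viral loads at 18 months. If survey completion at a visit were similarly low (an assumption; the documents do not give it), 275 × 0.60 = 165 women per arm would remain. The half-widths would then be 4.7, 6.5 and 8.6 points. This is why the number surveyed must be shown by arm and visit.

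**The case against.** **The DSMB already looks at violence.** Section 5.6 counts violence among adverse events, makes the review unblinded and asks for advice on imbalances. This stands in part: some by-arm look is foreseen, and nothing says Table 5.3 is everything the DSMB receives. But no statistic or denominator is set, nothing says survey answers feed the review, and a DSMB review is not a reported result.

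**The trial cannot say whether SMS raised violence.** A reader might infer this. It is too strong. Allocation is randomised and participant IDs link to arm, so a comparison is possible. What is missing is its pre-specification.

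**Violence disclosed in a survey would never reach the listing.** This too might be inferred, since the columns are labelled for SAEs. The documents do not support it: the table's title covers adverse as well as severe adverse events, and no text says whether a survey answer becomes an event.

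**The content and timing of the IPV items are not visible.** This stands. The survey topics are listed together, and section i of the Protocol defers the RCT instruments to a later modification. That IPV is asked at every visit and in every arm is an inference from the common questionnaire.

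**The route to harm may be weaker than it looks.** This also stands in part. The sample messages in the Protocol do not mention HIV or ART, another person reads messages only where the woman is comfortable with it, and the formative interviews with men sought concerns that could be met by changing messages. These steps lower the risk but do not measure it.

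**The SAP covers Aim 1 only.** This does not answer the point, because the SAP contains its own safety section. It does mean that absence from the SAP is no proof that the IPV data go unused elsewhere.

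**Conclusion.** The point holds as a gap in pre-specification and reporting. IPV is a planned survey topic and violence is a named harm, but the SAP plans no by-arm analysis of survey-reported IPV, and its one safety shell cannot show an imbalance. As planned, the trial would not report whether SMS changed violence. The efficacy analyses are unaffected.

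The size of any effect on violence is unknown. What can be sized is the precision of the missing estimate: about 4 to 7 points either side for one SMS arm v control. That rests on 248 women per arm, control IPV of 5% to 20% (assumed), and IPV being asked at follow-up in all arms (inferred). A reader might also suppose that women who leave care drop out of the survey altogether. The Protocol does not support that: women lost to follow-up are sought by home visit at study end, and 24-month procedures can be done there.

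**What to change.** 1. In SAP section 5.6, add a by-arm summary of adverse events and social harms: number of women affected, number of events and denominator.
2. For the follow-up visits at which the survey asks about IPV, add a descriptive safety table with the number surveyed and n and % reporting IPV, by arm and visit. Give a risk difference or risk ratio with 95% CI for one-way v control, two-way v control and either SMS arm v control. Adjust for enrolment IPV where collected, for example with a GEE. State that this is descriptive safety with no multiplicity adjustment.
3. Add enrolment IPV to Table 5.1.
4. Show surveys completed by arm and visit, counting 24-month home visits, because attendance may differ by arm.

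**Cost.** SAP wording, two added tables, one baseline row and one model. No new visits, staff or committee are needed. If the instruments turn out not to ask about IPV after enrolment, item 2 falls away and item 1 remains. The downside is one more unadjusted comparison of a self-reported measure in an unblinded trial, with limited precision. An interval that includes no difference should not be read as showing no harm.

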IDIs will be conducted by a Kenyan team trained in qualitative research methods and will probe for further elaboration on relevant content from the semi-structured IDI guide. Study investigators experienced in qualitative methods, [name] (site-PI) and [name] [name] (co-investigator), have reviewed topic guides for content validity and cultural relevance. We will also conduct surveys among male partners.

b) STUDY POPULATIONS**Female IDIs**

After completion of the RCT, we will invite 20 women from 1-way arm and 40 women from 2-way arm to participate in IDIs to understand reasons for success or failure of the intervention in supporting virologic suppression. Within each arm, sampling will be stratified based on VL and SMS engagement (see definitions below and Table 9). Participants will be samples from two study sites (1 in Kisumu and 1 in Nairobi).

Women who exit the RCT will be stratified based on two outcome variables:

- a. VL suppression
 - i. Participants with suppressed VL will be defined as:
 - Has ≥ 4 VL results available ≥ 6 mo post-ART initiation
 - ≥ 2 latest VL results < 1000 c/ml and ≥ 6 mo post-ART initiation
 - ≥ 1 earliest VL result ≥ 1000 c/ml and ≥ 6 mo post-ART initiation
 - ii. Participants with unsuppressed VL will be defined as:
 - Has ≥ 2 VL results available ≥ 6 mo post-ART initiation (fewer VL results needed so this group may have lower retention also)
 - ≥ 2 sequential VL results ≥ 1000 c/ml and ≥ 6 mo post-ART initiation and span ≥ 1 year
 - No ART resistance detected
- b. System engagement (among 2-way participants with more than 100 system messages and $\geq 90\%$ of these system messages successfully delivered)
 - i. Highly engaged participants will be defined as:
 - Participant's percent weeks active is $\geq 75^{\text{th}}$ percentile of all participants' percent of weeks active.
 - ii. Poorly engaged participants will be defined as:
 - Participant's percent weeks active is $\leq 25^{\text{th}}$ percentile of all participants' percent weeks active.

Table 9. Female IDIs sampling

Viral load	SMS interaction	site	n	
suppressed	High	Site 1 (Kisumu)	5	10
		Site 2 (Nairobi)	5	
	low	Site 1 (Kisumu)	5	10
		Site 2 (Nairobi)	5	
unsuppressed	high	Site 1 (Kisumu)	5	10
		Site 2 (Nairobi)	5	
	low	Site 1 (Kisumu)	5	10
		Site 2 (Nairobi)	5	
suppressed	NA (one-way)	Site 1 (Kisumu)	5	10
		Site 2 (Nairobi)	5	
unsuppressed	NA (one-way)	Site 1 (Kisumu)	5	10
		Site 2 (Nairobi)	5	
TOTAL				60

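### The Phase 3 rule for unsuppressed viral load has no condition on the latest results, so a woman suppressed at RCT exit can be sampled as a failure, and with an enrolment or routine viral load she can meet both definitions

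*Protocol*

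**What the plan says.** The Protocol (Phase 3, b) Study populations, Female IDIs) plans interviews with 20 women from the one-way arm and 40 from the two-way arm, "to understand reasons for success or failure of the intervention in supporting virologic suppression". Women leaving the RCT are stratified by viral load and, in the two-way arm, by SMS engagement.

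- The suppressed stratum (under "Participants with suppressed VL will be defined as") has three conditions. A woman needs four or more results from at least 6 months into ART. Her most recent ones must be low: "≥ 2 latest VL results < 1000 c/ml and ≥ 6 mo post-ART initiation". Her first such result must have reached 1000 c/ml.
- The unsuppressed stratum (under "Participants with unsuppressed VL will be defined as") also has three conditions. Two such results are enough, and resistance must not have been found. The viraemia condition reads: "≥ 2 sequential VL results ≥ 1000 c/ml and ≥ 6 mo post-ART initiation and span ≥ 1 year". The protocol explains the lower count of results: it lets in women with poorer retention.

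Table 9 puts the two strata in separate cells of 5 women per site. Table 10 labels them as success and failure and gives 60 as the maximum sample. No text says where to place a woman who meets both definitions.

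**The concern.** The suppressed rule is tied to the order of results: viraemic first, suppressed last. The unsuppressed rule can be met by results anywhere in follow-up, so viraemia that ended before exit still counts. A woman who was viraemic for a year and then became suppressed has the course that the suppressed rule describes, yet the text also admits her as a failure.

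The interviews are meant to contrast success with failure in cells of 5. If some of the failures had suppressed by exit, the contrast is blurred. If a woman fits both strata, her cell is left to whoever draws the sample.

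**Working it through.** **The plan's own figure.** Table 9: two-way arm 4 strata × 2 sites × 5 = 40; one-way arm 2 × 2 × 5 = 20; total 60. This reproduces and is not in dispute.

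**Inputs.**
- Visits are at enrolment, 6 weeks, and 6, 12, 18 and 24 months postpartum (Protocol, Phase 2, f) Data collection procedures). Blood for VL is drawn at all study visits (same section).
- Routine VLs are also abstracted (SAP Table 2.1).
- Women already on ART may enrol (Protocol, Phase 2, d) Recruitment procedures), so an enrolment VL can fall 6 months or more after ART start.
- Assumed for the check: all VLs are at least 6 months after ART start, visits occur on schedule, no resistance is found, and any routine VL is at 21 months.

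**Spans.** Six weeks is 42/30.44 = 1.38 months. From 6 weeks to 12 months is 12 − 1.38 = 10.6 months, under a year. From 6 to 18 months is exactly 12. From an enrolment VL as late as 36 weeks' gestation (about 0.92 months before a term birth) to 12 months postpartum is 12.9 months.

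**Enumeration.** Each VL was coded as at least 1000 or below 1000, and both definitions were applied to every possible pattern. The span condition can be read as an unbroken run of results at or above 1000 lasting a year (run), or as two adjacent results at least a year apart (adjacent pair).

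| VLs available | Reading | Unsuppressed patterns | of which latest VL <1000 | meeting both definitions |
|---|---|---|---|---|
| Five postpartum, complete | run | 6 of 32 | 2 | 0 |
| plus enrolment, complete | run | 14 of 64 | 5 | 1 |
| five plus one routine, complete | run | 10 of 64 | 4 | 1 |
| Same three, missed visits allowed | run | 42; 152; 124 | 8; 38; 40 | 0; 4; 6 |
| Same three, complete | adjacent pair | 0; 0; 0 | 0; 0; 0 | 0; 0; 0 |
| Same three, missed visits allowed | adjacent pair | 25; 87; 61 | 4; 17; 20 | 0; 1; 3 |

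Example of a failure suppressed at exit, from postpartum visits alone: at least 1000 at 6, 12 and 18 months, below 1000 at 24 months. Example meeting both definitions: at least 1000 at enrolment, 6 weeks, 6 and 12 months, below 1000 at 18 and 24 months.

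With the five postpartum VLs alone, no pattern meets both. The suppressed rule needs the two latest below 1000, so with later visits attended the viraemic run must end by 12 months, and 10.6 months is too short.

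**Frequency, as illustration only.** These are counts of patterns, not of women. A two-state model of 60,000 women was run. Missingness was 10% at 24 months and 40% at 18 months (SAP Table 6.1 gives 10% and over 40%). The other inputs are assumed: 20% missing at other postpartum visits, 15–25% viraemic at enrolment, 5% per interval becoming viraemic, 20–40% per interval re-suppressing.

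| Assumption | Last VL <1000, among unsuppressed | Meets both, among unsuppressed |
|---|---|---|
| Run reading, all enrolment VLs eligible | about 20–40% | about 5–12% |
| No eligible enrolment VL | about 10–20% | 0% |
| Re-suppression rate varies between women (beta, same mean, a+b=1) | about 5–11% | about 1–3% |
| Adjacent-pair reading | about 5–15% | about 0.4–2.5% |

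**After the fix.** If the unsuppressed rule also requires the two latest VLs to be at least 1000, no record can satisfy it and the suppressed rule together. The overlap is 0 under every schedule.

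**The case against.** The strongest reply is that failure need not mean viral load at exit. A year of viraemia without resistance, while receiving messages, is itself a failure to support suppression, and such a woman can say why. The lower count of results was clearly deliberate. This has force: a woman suppressed only at her last visit is arguably a legitimate interviewee. It does not explain why one stratum is defined by its latest results and the other is not, or where a woman who fits both belongs.

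The reply on wording also stands in part. Under the adjacent-pair reading the problem is smaller, but under that reading no woman with complete 6-monthly results could be unsuppressed, so the run reading is the more natural one.

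A reader might infer that one or two of every five interviewed failures would have been suppressed at exit. The documents do not support that. It takes the upper rows of a simulation whose inputs are mostly assumed, ignores the resistance condition, and treats purposive selection as a random draw. Nor do the documents show that any woman actually met both definitions. That requires an eligible enrolment VL or an extra routine one, and an ARV-naive woman's enrolment VL cannot count.

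**Conclusion.** The gap holds as a property of the written rule. The unsuppressed definition can admit women whose latest VL is below 1000. The two strata are not mutually exclusive once enrolment or routine VLs are used, and the documents provide for both. The frequency cannot be found from the documents. Depending on assumptions, the simulations span about 5% to 40% of unsuppressed women with a last VL below 1000, and 0% to 12% meeting both definitions.

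Severity is minor. A reader might extend the point to the trial's virologic results, but the SAP's Aim 1 endpoints and analyses do not use these strata. Only the sampling of the post-RCT interviews is affected.

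**What to change.** In the Phase 3 definition, state that the one-year span means an unbroken run of results at or above 1000 c/ml, and require that run to include the latest VLs, with the two latest both at least 1000. The minimum of two results can stay, so women with poor retention remain eligible. This is one line in the protocol and one in the sampling query.

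The cost is a smaller pool. In the simulations about 20% to 40% of unsuppressed women drop out under the run reading when all enrolment VLs are eligible. Cells may already be thin. If recruitment follows the anticipated monthly numbers (four sites at 20 and two at 35, total 150), a site supplies 275 × 20/150 = 37 to 275 × 35/150 = 64 women per arm. With 8–18% unsuppressed, as in the model, and a quarter of them in each engagement group, a two-way cell holds about 37 × 0.08/4 = 0.7 to 64 × 0.18/4 = 2.9 women before any change. Some cells may therefore fall short of 5. That is tolerable because 60 is stated as a maximum.

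If cells cannot be filled, the minimum is to exclude from the unsuppressed stratum any woman who meets the suppressed definition, and to record each interviewee's exit VL. This removes dual membership and leaves late suppression visible when the interviews are read.
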